**Experimental design:** We will screen up to 45 participants to accrue a total of 38 participants [ 14 individuals with normal weight (BMI 20-25), 24 individuals with obesity (BMI >30)] to compare bile acid pathway, key elements of the enterohepatic bile acid regulation and incretin pathway at three different metabolic stages: 1) at baseline, 2) on a 100 grams of fat diet, and 3) on a low calorie, low fat diet. Participants will be on each diet for 7 days prior to collection of samples; with one week on regular diet between the high fat/calorie diet and the low calorie diet. Fasting and postprandial blood samples will be used to analyze, metabolomics, PYY, GLP-1, FGF-19, C4, BA, and short-chain fatty acids (SCFA) on test days. Saliva sample will be collected for GI peptides and metabolomics. Visual analog scale (VAS) ratings of appetite and satiation will be recorded during the day (on the same days) every 15 minutes for the first 90 minutes, then every 30 minutes. On day 5 and 6 (48 hours), stool from every bowel movement will be collected for fecal BA, SCFA and microbiome. Participants will repeat the stool collection and above studies for a total of three times. On day 5 of 1st, 2nd and 4th week, participants will undergo a flexible sigmoidoscopy with biopsies.

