## STATISTICAL ANALYSIS

**Endpoints:** *Primary endpoint:* Fecal BA excretion in obesity vs. health and the change from baseline with high fat/high calorie diet vs. low calorie diet. *Secondary endpoints:* (a) fecal individual BA and SCFA excretion; (b) fasting serum C4 and FGF19; (c) serum BA; and (d) serum fasting, peak and AUC postprandial FGF-19, GLP-1 and PYY.

**Statistical analysis:** The proposed analyses are based on analysis of covariance models, with the responses being each variable compared to baseline. The covariates to be considered include gender and BMI.

**Sample size:** In healthy volunteers, the normal value for fecal BA is  $957 \pm 185$  micromoles/48hours (SEM). The table below summarizes data for primary endpoint considering the mean difference between two groups (healthy vs. obesity) and difference between baseline to high fat vs. low fat diet in each group (healthy vs. obesity), n=8 per group; and estimates the effect size detectable with 80% power based on a two sample t-test at a two-sided  $\alpha$  level of 0.05. We will accrue 38 participants to achieve the above given n value, assuming a 20% dropout rate.

Response	Mean	SD	Predicted differences [% (absolute #)] n=8/group
Fecal BA, $\mu$ moles/48hours	957	185	1) Patient with obesity compared to health: 25% (258 $\mu$ moles/48h) 2) Baseline compared to high fat vs. low fat diet: 24% (233 $\mu$ moles/48h)

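### The detectable diet difference of 233 µmol/48h does not follow from the stated two-sample t-test (259 to 279), and the within-person diet contrast has no variance basis or linked analysis

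*Combined protocol and SAP*

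**What the plan says.** All of this is in the STATISTICAL ANALYSIS section unless noted.

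- **Endpoint.** The primary endpoint is fecal bile acid excretion. It has two parts: obesity versus health, and "the change from baseline with high fat/high calorie diet vs. low calorie diet".
- **Sample size.** One sentence covers the group difference and the "difference between baseline to high fat vs. low fat diet in each group (healthy vs. obesity), n=8 per group", and it "estimates the effect size detectable with 80% power based on a two sample t-test" at a two-sided 0.05 level. The table has a single row of inputs (mean 957, SD 185, n = 8 per group) and two results: 258 µmol/48h for obesity versus health, and "Baseline compared to high fat vs. low fat diet: 24% (233" µmol/48h).
- **Spread.** The text gives the healthy-volunteer value as 957 ± 185 "micromoles/48hours (SEM"). The table lists the same 185 under SD.
- **Accrual.** "We will accrue 38 participants to achieve the above given n value, assuming a 20% dropout rate". The split is 14 normal weight and 24 obesity.
- **Analysis.** "The proposed analyses are based on analysis of covariance models, with the responses being each variable compared to baseline". The covariates named are gender and BMI.
- **Design.** The ABSTRACT states: "Participants will repeat the stool collection and above studies for a total of three times". The APPROACH section and its schedule agree: each person has a stool collection at baseline, on the high-fat diet and on the low-calorie diet.

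**The concern.** Two results are reported from one set of inputs, and they differ. The same test, n, SD, power and alpha cannot give both 258 and 233, so the second figure used something the plan does not state.

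The named test also does not match the comparison. Within each weight group, the high-fat and low-calorie measurements come from the same people. The detectable difference then depends on the SD of the within-person change, or equivalently on an SD and a within-person correlation. Neither is given. The analysis sentence does not say how the two diet responses of one person will be linked.

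The 233 figure is the plan's only statement of what the diet half of the primary endpoint can detect. If it is unreliable, a reader cannot judge whether the study is adequate for that half, and the choice of model for a primary comparison is left open until analysis.

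**Working it through.** **Inputs from the plan:** SD 185 (as labelled in the table), n = 8 per group, two-sided alpha 0.05, power 80%, accrual 14 and 24, dropout 20%.

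**Assumptions not in the plan:** equal SD and equal correlation r across the three stages, with r from 0 to 0.7; dropout falling equally on both groups, giving 14 × 0.8 = 11.2 (about 11) and 24 × 0.8 = 19.2 (about 19) completers.

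**1. The plan's own calculation.**

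- Normal approximation: (1.960 + 0.842) × 185 × √(2/8) = 259.1.
- Exact (non-central) t, 14 df: 278.7.

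The 258 in the first row agrees with the normal value to rounding. The 233 in the second row agrees with neither: the correct values are 11% (259.1/233) to 20% (278.7/233) higher. Power at 233 is 71.2% (normal) or 64.9% (t). Reaching 80% at 233 would take 10 (normal) or 11 (t) per group.

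**2. Can 233 be recovered another way?**

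| Variant (SD 185 unless noted) | Detectable difference |
|---|---|
| One-sided two-sample, n = 8 | 230 (normal), 242 (t) |
| Two-sample t, 11 per group | 232.4 |
| Two-sample normal, 10 per group | 231.8 |
| Paired t, n = 8, r = 0.3 | 253 |
| Paired t, n = 8, r = 0.5 | 214 |

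A paired t-test at n = 8 gives 233 when the SD of change is about 202, which means r of about 0.41. A comparison of diet change between the weight groups at n = 8 per group gives 233 when the SD of change is 233/278.7 × 185 = 155 (t) or 233/259.1 × 185 = 166 (normal). Each route needs an n, a correlation, an SD of change or a sidedness that the plan does not state.

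**3. Paired contrast if 185 is an SD.** SD of difference = 185 × √(2(1 − r)). The paired t-test at 80% power detects 0.938 × that SD with n = 11 and 0.680 × that SD with n = 19.

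| r | SD of difference | Detectable, n = 11 | Detectable, n = 19 | Power at 233, n = 11 | Power at 233, n = 19 |
|---|---|---|---|---|---|
| 0 | 261.6 | 245 | 178 | 76% | 96% |
| 0.3 | 218.9 | 205 | 149 | 89% | 99% |
| 0.5 | 185.0 | 173.5 | 126 | 96% | >99% |
| 0.7 | 143.3 | 134 | 97 | >99% | >99% |

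**4. How large the SD may be.** The largest SD that keeps 80% paired power at 233 is 185 × 233 / (detectable difference). For r = 0, 0.3, 0.5, 0.7 this is 176, 210, 249, 321 with 11 completers and 242, 290, 343, 443 with 19.

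**5. Paired contrast if 185 is an SEM.** Then SD = 185 × √m, where m is the size of the cited study, which the plan does not give. For an assumed m of 5, 10 and 30 the SD is 414, 585 and 1013. Over r = 0 to 0.7 the paired detectable difference is:

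- m = 5: 549 to 300 with 11 completers, 398 to 218 with 19.
- m = 30: 1344 to 736 with 11 completers, 974 to 533 with 19.

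**6. What linking the two responses is worth.** This is conditional, because the plan does not say the responses will be treated as independent. If they were, the standard error of the diet contrast would be overstated by √[4(1 − r) / 2(1 − r)] = 1.41 for change scores at any r. For baseline-adjusted ANCOVA the factor is √[(1 − r²)/(1 − r)] = √(1 + r), which is 1.14, 1.22 and 1.30 at r = 0.3, 0.5 and 0.7.

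**The case against.** The strongest reply is that nothing is shown to be underpowered. If 185 is an SD, as the table says, a paired test detects 233 or less in almost every case. The exception is the normal-weight group with r below about 0.1. On that reading 233 is mostly conservative. This stands, and it limits the severity.

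Second, 233 may be a correct figure with a wrong description: a paired test at n = 8 with r of about 0.41, or a two-sample t-test with 11 per group. Either is possible, and the documents cannot show which input was misreported. Neither rescues the text, which states n = 8, a two-sample test and no correlation.

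Third, the analysis sentence relates each response to baseline, so each person's own baseline does enter. If each diet's change were analysed in a separate model, there would be one response per person and no person term would be needed. That is a fair reading of the sentence. However, the primary endpoint sets one diet's change against the other's, and separate models do not test that. The gap is one of under-specification, and ignoring the pairing would make the contrast conservative rather than falsely positive.

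Fourth, the large figures in step 5 depend on the SEM reading and on an assumed source-study size, and the SD/SEM conflict affects both table rows. That is correct. Those figures show how uncertain the plan's sensitivity is; they do not estimate it.

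**Conclusion.** The point holds. On the plan's stated inputs the detectable diet difference is 259 to 279 µmol/48h, and power at 233 is 65% to 71%. This part needs no assumption beyond taking 185 as an SD, as the table does.

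For the paired contrast that the design actually provides, the plan lacks the variance inputs and does not say how one person's responses are linked. With 185 as an SD, about 11 and 19 completers and r from 0 to 0.7, the detectable difference is 245 to 134 in normal weight and 178 to 97 in obesity. No power loss is shown there at moderate correlation. With 185 as an SEM, it exceeds 233 at most of the inputs examined. The reader cannot tell which case applies. The sponsor should correct this, but it does not by itself show that the study is too small.

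**What to change.** 1. Check the cited source for whether 185 is an SD or an SEM, and correct the label in the text or the table.
2. State in the STATISTICAL ANALYSIS section that high fat versus low calorie is a within-person contrast. Name its analysis: a paired test within each weight group, or a repeated-measures model with a person term, diet stage, weight group and the stage-by-group interaction.
3. Replace 233 with the paired detectable difference at the expected completers (about 11 and 19), giving the SD and the correlation assumed. Use the SD-based ranges in the verdict only if 185 is confirmed as an SD; otherwise recompute from the source SD.
4. If the second row was meant to compare diet change between the weight groups, say so and give the SD of change used.

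The cost is a text change and one look-up, with no added participants, visits or procedures. The new figure will rest on an assumed correlation, so it should be given as a range or supported by the team's own repeat measurements. If 185 proves to be an SEM, the restated difference will probably be larger than 233.

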**Experimental design:** We screen up to 45 participants and will study a total of 38 participants[ 14 individuals with a normal weight (BMI 18.5-25), 24 individuals with obesity (BMI >30)] to compare bile acid pathway, key elements of the enterohepatic bile acid regulation and incretin pathway in obesity compare to health (normal weight) at three different metabolic stages: 1) at baseline, 2) on a 100 grams of fat diet, or 3) on a low calorie, low fat diet. Participants will be on each diet for one week prior to collection of samples; with one week on regular diet between the high fat/high calorie diet and the low calorie diet. Diet will be provided by the metabolic kitchen. Participants will present after an overnight fast to the CRTU on day 5 and day 7 for testing. On day 5 participants will undergo a flexible sigmoidoscopy procedure from which a biopsy will be obtained. A bowel cleansing with water enema will be given by a CRTU nurse before the procedure. On day 7, participants will consume their "scheduled meal" and blood samples will be collected at -15, 0, 15, 30, 45, 60, 90, 120, 150, 180, 210, 240, 300, 360 minutes. Fasting and postprandial blood samples will be used to analyze, metabolomics, PYY, GLP-1, FGF-19, C4, BA, and short-chain fatty acids (SCFA). Plasma will be collected to analyze EV. Fasting saliva sample will be collected for GI peptide and metabolomics. VAS ratings of appetite and satiation will be recorded during the day every 15 minutes for the first 90 minutes, then every 30 minutes. Prior to discharge from the CRTU, participants will meet with study staff to discuss the following week's diet. On day 5 and 6 (48 hours), stool from every bowel movement will be collected for fecal BA, SCFA and microbiome. Participants will repeat the studies for a total of three times.

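### The detectable diet effect of 233 µmol/48h does not follow from its stated inputs, and this within-person contrast needs an SD of change that the plan does not give

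*Combined protocol and SAP*

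**What the plan says.** STATISTICAL ANALYSIS, Endpoints, makes fecal bile acid excretion primary in two respects: obesity against health, and change from baseline on the high fat diet against the low calorie diet.

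The Sample size paragraph "estimates the effect size detectable with 80% power based on a two sample t-test", two-sided at 0.05. The table beneath it has one mean (957), one SD (185) and one column, headed "Predicted differences [% (absolute #)] n=8/group". That column holds two entries:
- Row 1: "Patient with obesity compared to health: 25% (258" µmol/48h).
- Row 2: "Baseline compared to high fat vs. low fat diet: 24% (233" µmol/48h).

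The paragraph places the row 2 contrast inside each of the two groups. It gives no within-person correlation and no SD of change. It labels 185 an SEM in the sentence and an SD in the table.

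On design, APPROACH, Experimental design, says: "Participants will repeat the studies for a total of three times". The schedule table and the METHODS visit list (visits 3, 5 and 8) also take each participant through baseline, high fat and low calorie weeks. Planned enrolment is 14 normal weight and 24 obesity, with 20% dropout assumed.

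The analysis paragraph names analysis of covariance on each variable compared with baseline, with gender and BMI as candidate covariates.

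**The concern.** One test with one n, SD, alpha and power has one detectable difference. Two printed values mean that at least one rests on something the plan does not state.

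The named test also does not fit row 2. A contrast between diet stages in the same people has its precision set by the spread of the within-person difference, not by the spread between people at one visit. The two are linked by the within-person correlation, which is absent.

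The figure of 233 is the only stated sensitivity for the diet half of the primary endpoint. As written, a reader cannot tell what diet effect the study can detect, or whether a null result would be informative.

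**Working it through.** **Inputs** (STATISTICAL ANALYSIS, Sample size): n = 8 per group, SD = 185 as labelled in the table, two-sided alpha 0.05, power 80%, two-sample t-test. Enrolment of 14 and 24 is from APPROACH, Experimental design. The within-person correlation rho is not given, so it is varied as an assumption.

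**1. The stated calculation.**
- Normal approximation: 185 × sqrt(2/8) × (1.960 + 0.842) = 259.1. This is close to the 258 in row 1.
- Exact noncentral t, 14 df: 1.5066 × 185 = 278.7, which is 29% of 957.
- Neither gives 233.

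**2. Power at the printed values.** The standard error is 185 × sqrt(2/8) = 92.5.
- At 233: noncentrality 233/92.5 = 2.52; power 64.9% (exact t) or 71.2% (normal).
- At 258: noncentrality 258/92.5 = 2.79; power 73.7% (exact t) or 79.7% (normal).
- Row 1's percentage is also off: 258/957 = 27.0%, not 25%. Row 2's is right: 233/957 = 24.3%.

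**3. What would produce 233.** Values near it appear only when a stated input is changed:
- two-sample t with 11 per group: 232.4
- normal approximation with 10 per group: 231.8
- one-sided normal approximation with 8 per group: 230.0

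Reading 185 as the SD of the within-person difference does not rescue it: a paired t-test at n=8 then gives 213.9.

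**4. Paired calculation.** The contrast (high fat − baseline) − (low calorie − baseline) reduces to high fat − low calorie in the same person. With a common SD at each stage, SD of difference = 185 × sqrt(2(1 − rho)). At n=8 the exact paired t-test detects 213.9/185 = 1.156 SDs of the difference. For 233 the SD of the difference must be 233/1.156 = 201.6, so rho = 1 − (201.6/185)²/2 = 0.41.

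**5. Expected completers.** 14 × 0.8 = 11.2 and 24 × 0.8 = 19.2, so about 11 and 19. Paired detectable differences (µmol/48h, SD 185, 80% power):

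| rho | n=8 | n=11 | n=19 |
|---|---|---|---|
| 0 | 302.5 | 245.3 | 177.8 |
| 0.3 | 253.1 | 205.3 | 148.8 |
| 0.5 | 213.9 | 173.5 | 125.7 |
| 0.7 | 165.7 | 134.4 | 97.4 |

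At n=11, 233 is reached once rho is about 0.10 (245.3 × sqrt(0.9) = 232.7). At n=19 it is reached even at rho = 0. For row 1, the two-sample t-test with 11 versus 19 detects 203.4.

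**6. If 185 is an SEM.** The SD is then 185 × sqrt(m), where m is the size of the source sample, which is not given. For an assumed m of 8 to 30 the SD is 523 to 1013, and the two-sample detectable difference at 8 per group is 788 to 1527. The paired figures scale in the same way: at rho 0.5 and m = 8, 173.5 and 125.7 become about 491 and 356 (× 2.828).

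**The case against.** **Enrolment exceeds 8 per group.** A reader might infer from the 65% that the trial is underpowered for the diet effect. The documents do not support that. The 65% belongs to the stated calculation, not to the planned sample. Two groups of 8 with 20% dropout would need 16/0.8 = 20 people, yet 38 are planned. Even the stated two-sample test detects 232.4 at 11 per group. This objection stands for as long as the SD is 185.

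**An unpaired analysis is not planned.** A reader might also infer that a two-sample test will be run on the two change scores, losing the pairing and possibly missing a real effect. The two-sample t-test is named only for sample size; the stated analysis is covariance analysis on values compared with baseline. That analysis is thinly described, but nothing in it says the pairing will be ignored. This objection stands.

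**Row 2 might mean something else.** If it compares diet change between obesity and health, a two-sample test is legitimate, but with the SD of change. Then 233 at 8 per group needs an SD of change of 233/1.5066 = 154.6, or rho of about 0.65, which is also unstated. The paragraph places the contrast in each group, so the within-person reading is the more natural one. Parts of APPROACH join the two diets with "or", but the schedule and visits put everyone through both. What stands is that the contrast should be named.

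**The error may be conservative.** With rho above 0.41, the paired value at n=8 is below 233. This is true, but the printed figure still cannot be derived.

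**Conclusion.** The point holds as an error in the stated sensitivity and a missing assumption. On the stated inputs the detectable difference is 279 (259 by normal approximation), not 233, and power for 233 is 65% (71%). The row 1 value of 258 agrees with the normal approximation but has 74% power under the named t-test. On the within-person reading, 233 at n=8 needs rho of about 0.41, which the plan does not state.

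The point does not extend to a shortfall in the trial's power. With SD 185, equal at each stage, and about 11 and 19 completers, paired detectable differences are 205 and 149 at rho 0.3, 174 and 126 at 0.5, and 134 and 97 at 0.7, all below 233. That reassurance depends on 185 being an SD. If it is an SEM, every detectable difference grows by the square root of the source sample size, and the documents do not allow a conclusion about power in either direction.

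**What to change.** In STATISTICAL ANALYSIS, Sample size, in this order:

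1. State whether 185 is an SD or an SEM. If it is an SEM, give the source sample size and convert before computing anything else. The figures below apply only if the SD is 185.
2. Name the diet contrast, for example within-person high fat minus low calorie fecal bile acid excretion, estimated in each group.
3. Replace row 2 with a paired calculation that states the assumed SD of change, or a range of rho, for the expected completers in each group. At SD 185 these are about 205 and 149 (rho 0.3), 174 and 126 (0.5), and 134 and 97 (0.7).
4. Limit the two-sample t-test to row 1 and recompute that row: 279 at 8 per group, or about 203 at 11 versus 19. Correct its percentage to match.

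The cost is one rewritten paragraph and two recalculated rows, with no change to participants, visits or diets. Any figures kept at n=8 may look less favourable: row 1 rises from 258 to 279, and row 2 exceeds 233 if rho is below about 0.41. If 185 proves to be an SEM, the adequacy of the sample becomes a separate question to answer with the corrected SD.

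### The sample-size statement does not follow from its own inputs: 185 is labelled both SEM and SD, n = 8 per group with 20% dropout gives 20 rather than 38, and 258 is 27% of 957, not 25%

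*Combined protocol and SAP*

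**What the plan says.** All of this stands in the Statistical Analysis section, under Sample size, unless noted.

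- **Spread.** The healthy-volunteer fecal bile acid value is 957 ± 185, labelled "micromoles/48hours (SEM" in the text. The table prints the same 185 under a column headed SD.
- **Method.** The paragraph "estimates the effect size detectable with 80% power based on a two sample t-test at a two-sided" level of 0.05. The table column is headed "Predicted differences [% (absolute #)] n=8/group".
- **Differences.** The first is "Patient with obesity compared to health: 25% (258" µmol/48h); the second is "Baseline compared to high fat vs. low fat diet: 24% (233" µmol/48h). The text describes the second as the "difference between baseline to high fat vs. low fat diet in each group (healthy vs. obesity), n=8 per group".
- **Accrual.** "We will accrue 38 participants to achieve the above given n value, assuming a 20% dropout rate".
- **Design.** The Experimental design paragraphs of the Abstract and the Approach split the 38 into 14 normal-weight participants and 24 with obesity, and have every participant studied three times.
- **Analysis.** The Statistical analysis paragraph plans covariance models: "The covariates to be considered include gender and BMI".

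**The concern.** An SEM and an SD differ by the square root of the source sample size, so one number cannot carry both labels unless the source had a single subject. The spread converts a standardised effect into µmol/48h, so the label decides what difference the primary endpoint can detect.

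The other parts of the statement also fail to connect. The accrual figure does not come from the stated group size and dropout. One percentage does not match its absolute difference. The named test does not give the printed 258. The diet difference is within-person but is assigned a two-sample test, with no within-person SD or correlation.

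**Working it through.** **Inputs from the documents:** mean 957; spread 185; n = 8 per group; two-sided 0.05; 80% power; two-sample t-test; 20% dropout; 38 enrolled as 14 and 24. **Assumed:** a common SD in both weight groups, no covariate adjustment, and, for the SEM reading, the size m of the cited source.

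**1. Percentages.** 258/957 = 27.0%; 25% of 957 is 239. 233/957 = 24.3%, which agrees with the printed 24%.

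**2. Accrual.** Two groups of 8: 16/(1 − 0.20) = 20 (or 16 × 1.2 = 19.2). Four cells of 8 (weight group by diet): 32/0.8 = 40, or 32 × 1.2 = 38.4. Only the unstated four-cell layout comes near 38.

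**3. The plan's 258, taking SD = 185 and 8 per group.**
- Normal approximation: 185 × (1.960 + 0.8416) × √(2/8) = 259.1, close to 258.
- Named t-test (noncentral t, 14 df): 1.507 SD × 185 = 278.7, or 29.1% of 957. Its power for 258 is 73.7%.

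**4. The plan's 233.** The two-sample t-test at 8 per group, applied literally, has 64.9% power for 233. It gives 232.4 at 11 per group, which is not the stated n. For a paired test, the SD of the difference is SD × √(2(1 − ρ)), assuming equal variance across diets. With n = 8 the detectable difference is 1.156 of these SDs: 271, 234 or 135 for ρ = 0.2, 0.4 or 0.8 at SD 185. No ρ is given, so 233 can be neither confirmed nor refuted.

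**5. Between-group comparison as enrolled.** 14 × 0.8 = 11.2 and 24 × 0.8 = 19.2, so about 11 and 19 evaluable. The noncentral t gives 1.10 SD (1.0996) at 80% power.

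If 185 is an SD: 1.0996 × 185 = 203 (21% of 957), with 94% power for 258. If dropout is unequal (30 evaluable, from 14/16 to 6/24), the detectable difference is 1.06 to 1.32 SD, or 197 to 245, and power for 258 is 96% to 84%.

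If 185 is an SEM: SD = 185 × √m, with 11 and 19 evaluable.

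| Source size m (assumed) | SD | Detectable difference | Power for 258 |
|---|---|---|---|
| 2 | 262 | 288 | 71% |
| 5 | 414 | 455 (48% of 957) | 36% |
| 10 | 585 | 643 | 20% |
| 20 | 827 | 910 | 12% |
| 30 | 1013 | 1114 (116% of 957) | 10% |

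80% power for 258 needs an SD of at most 258/1.0996 = 235, that is m = (235/185)² ≈ 1.6. So after the planned dropout, power is below 80% for any source of two or more people.

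**6. Paired diet contrast as enrolled.** The detectable difference is 0.94 SD of the within-person difference for n = 11 and 0.68 for n = 19. At SD 185 and ρ = 0.2, 0.5 or 0.8 this is 219, 173 or 110 (n = 11) and 159, 126 or 80 (n = 19). If 185 is an SEM, multiply by √m.

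**The case against.** Five points can be made for the plan.

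- **The planner evidently used 185 as an SD,** since 258 is almost exactly the normal-approximation value at n = 8. This is a fair inference about the calculation, but it does not show that the cited source reports an SD. If the text label is right, the calculation used the wrong quantity.
- **The low-power figures rest on an assumed source size.** They do. They are scenarios, and the case m = 2 shows that little depends on the exact choice once dropout is allowed for. With no dropout at all (14 and 24), power for 258 is 81% at m = 2 and 64% at m = 3.
- **38 may come from four cells of 8.** The Approach section in places words the two diets as alternatives, which could be a remnant of that layout. But no such design is stated, every participant is to be studied three times, and 16 normal-weight completers cannot come from 14 enrolled. The mismatch is harmless in direction: about 11 and 19 completers exceed 8 per group.
- **The diet difference might mean comparing change between weight groups,** for which a two-sample test would fit. The words about each group favour the within-person reading. On either reading an SD of change is needed and is missing.
- **The percentage, and t-test versus normal approximation, change nothing as enrolled.** Agreed; these are drafting faults. The BMI covariate belongs mainly to the analysis model and matters here only as a caveat on the unadjusted figures.

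**Conclusion.** The concern holds. The statement contradicts itself on the spread, its 38 does not follow from its stated n and dropout, and its 25% should be 27% for the printed 258. The consequential fault is the SEM/SD label. Taken as an SD, 185 leaves the obesity-versus-health comparison with 84% to 96% power for 258 however the eight expected dropouts fall. Taken as an SEM, it leaves that power below 80% after the planned dropout for any source of two or more people.

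This does not establish that the trial is underpowered; the documents cannot settle which reading is right. If 185 is an SD, the remaining items cost no power at the enrolled size. The figures assume a common SD in the two weight groups and no adjustment for BMI.

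**What to change.** 1. Establish from the cited source whether 185 is an SD or an SEM. If it is an SEM, convert with that source's n (SD = 185 × √n). Use one label in text and table.
2. Restate the between-group detectable difference for the real accrual: 14 and 24, about 11 and 19 evaluable, noncentral t, 1.10 SD. Give it in µmol/48h only with the confirmed SD. State that equal dropout is assumed (1.06 to 1.32 SD otherwise) and that the figure is not adjusted for BMI. The weight groups are non-overlapping BMI ranges, so adjusting for BMI could make 1.10 SD optimistic.
3. State which diet contrast is meant. For the within-person contrast, replace the two-sample calculation with a paired one per group: 0.94 SD of the difference for n = 11 and 0.68 for n = 19. Give the assumed correlation with a range, for example 0.2 to 0.8, and state the equal-variance assumption.
4. Make the percentage agree with the absolute difference, and stop presenting 38 as the result of 8 per group with 20% dropout.

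The cost is one check of the cited source and a rewrite of one paragraph and one table. No change to enrolment or procedures is proposed.
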